2 OVERALL STUDY DESIGN, OBJECTIVES AND OUTCOMES

2.1 Study design

Cardiol 100-004 was designed as a multi-center, open label Pilot Study. The trial protocol planned that approximately 25 patients would be enrolled.

2.2 Study Objectives

The primary objective was to evaluate the effect of treatment with CardiolRx™ on recurrent pericarditis.

The primary safety objective was to demonstrate that administration of CardiolRx™ in the proposed doses in this patient population is safe.

2.3 Study endpoints

2.3.1 Primary efficacy endpoints

The primary efficacy endpoint was the change in patient-reported pericarditis pain using an 11-point NRS from baseline (highest pain score within the past 7 days of Day 1) to Week 8 (highest pain score during the past 7 days of the Week 8 visit).

2.3.2 Additional efficacy endpoints of interest

Per section 4.1.3 of the study protocol (Amendment 2), additional efficacy endpoints are:

- Pain score using 11-point NRS from baseline (highest pain score within the past 7 days of Day 1) to Week 26 (highest pain score during the past 7 days of Week 26)
- - Percentage of patients with normalized CRP levels at 8 weeks (for patients with CRP ≥ 1.0 mg/dL at baseline)
- - Percentage of patients with pericarditis recurrence during the EP
- - Percentage of patients with normalized CRP levels at 26 weeks (for patients with CRP ≥ 1.0 mg/dL at baseline)
- - Time to CRP normalization for patients with CRP ≥ 1.0 mg/dL at baseline
- - CRP change from baseline at 26 weeks (%)

2.3.3 Additional efficacy endpoint of interest in Protocol amendment 2

Compared to protocol version 1, the endpoint 'Percentage of patients with pericarditis recurrence during the extension period (EP)' was added in protocol amendment 2.

Impact on statistical Analysis Plan:

Given that the data to ascertain this outcome will be available for all enrolled patients, there is no impact on the SAP / analysis for this additional endpoint added per protocol amendment 2.

2.3.4 Safety endpoints

Per section 4.2.2 of the study protocol (Amendment #2), the safety outcomes will encompass the following:

- Occurrence of adverse / serious adverse events as of the start of the IMP through the last study visit.

- Change (from baseline) in C-SSRS at the end of patient follow-up – i.e. either at week 8 or week 26-week study visit.
- Change (from baseline) in laboratory parameters, including liver function parameters and INR at the end of patient follow-up – i.e. either at the week 8 or the week 26 study visit.
- Change (from baseline) in ECG intervals/findings parameters at the end of patient follow-up – i.e. either at the week 8 or the week 26-week study visit.

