#### 4.2.2 Safety Parameters

Safety parameters include the number of AEs and SAEs, changes in C-SSRS as well as changes in laboratory parameters, including liver function parameters and INR as well as ECG intervals and rhythm during the 26-week study period.

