### **9.2.10    C-SSRS**

The C-SSRS is a questionnaire designed for the assessment of suicidal ideation and behavior in adolescents and adults.

To monitor for the emergence of suicidal ideation and behavior, patients will undergo C-SSRS evaluations at baseline, at Week 8 and at Week 26.

The questionnaire must be administered by an investigator or other individual that is suitably qualified by education or training. See Appendix 17.4 for a sample C-SSRS - Baseline/Screening version assessment and Appendix 17.5 for a sample post-dose C-SSRS assessment.

If a patient becomes suicidal during the study, an investigator or medically qualified sub-investigator should provide the appropriate treatment to the patient.

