8.6.3 Change in C-SSRS

The number of patients with C-SSRS ideation and behaviour scores compared to baseline will be summarized.

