Table 29 – Patients with a worsening of C-SSRS ideation and behaviour scores compared to baseline

Table 30 – Laboratory tests results (absolute and change from baseline) during the 26-week study period – Descriptive statistics

Table 31 – Patients who experience changes in laboratory parameters during the 26-week study period

Table 32 – ECG intervals (absolute and change from baseline) during the 26-week study period – Descriptive statistics

Table 33 – Vital signs (absolute and change from baseline) during the 26-week study period – Descriptive statistics

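### SAP 2.3.4 limits the C-SSRS outcome to the final visit, which is narrower than protocol 4.2.2, so a Week 8 worsening that has resolved by Week 26 may go unreported

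*SAP*

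**What the plan says.** **Protocol.** Section 4.2.2 lists the parameter: "Safety parameters include the number of AEs and SAEs, changes in C-SSRS", together with laboratory changes, and ends the list with "ECG intervals and rhythm during the 26-week study period". Section 9.2.10 gives the purpose as watching for emerging suicidal ideation and behaviour, and sets the timing: "patients will undergo C-SSRS evaluations at baseline, at Week 8 and at Week 26". It names the follow-up form by pointing to "Appendix 17.5 for a sample post-dose C-SSRS assessment". That appendix reproduces the Since Last Visit version of the scale.

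**SAP.** Section 2.3.4 says it follows protocol 4.2.2 and then defines the outcome as "Change (from baseline) in C-SSRS at the end of patient follow-up – i.e. either at week 8 or week 26-week study visit". The laboratory and ECG outcomes in the same list are limited in the same way. The analysis text for C-SSRS, section 8.6.3, is a single sentence: "The number of patients with C-SSRS ideation and behaviour scores compared to baseline will be summarized". The only planned follow-up output is Table 29: "Patients with a worsening of C-SSRS ideation and behaviour scores compared to baseline". Neither names a visit. By contrast, section 8.6.4 presents laboratory values by time point, section 8.6.5 describes ECG change over the 26 weeks, and Tables 30 and 32 carry that through.

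**The concern.** The schedule has two post-baseline C-SSRS assessments. The SAP outcome uses one per patient: Week 8 for those who finish there and Week 26 for those followed to the end of the extension. In the second group, a patient who was worse than baseline at Week 8 and back to baseline at Week 26 is not a case under 2.3.4.

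Week 8 is not a redundant reading. It follows the whole dose-escalation period. It is also the only post-baseline C-SSRS scheduled before background pericarditis therapy is weaned, because weaning starts at Visit 5 for patients entering the extension (protocol 6.2 and 9.1). Monitoring for emergence should register a transient event. A final-visit definition is the one most likely to miss it.

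At stake is the reported count for a named safety parameter in a pilot whose safety objective is to show that the proposed doses are safe. The data needed are already collected.

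**Working it through.** The documents give no figure to reproduce. The check compares texts and counts coverage.

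**1. Which visit counts under SAP 2.3.4**

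| Patient | C-SSRS collected after baseline | Used under 2.3.4 | Not used |
|---|---|---|---|
| Finishes at Week 8 | Week 8 | Week 8 | none |
| Followed to Week 26 | Week 8, Week 26 | Week 26 | Week 8 |
| Enters extension, no Week 26 C-SSRS | Week 8 | no rule stated | unclear |

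**2. Does a later SAP section restore Week 8?**

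| Outcome | SAP 2.3.4 | Analysis section | Table |
|---|---|---|---|
| Laboratory | final visit | 8.6.4: by time point | 30: over 26 weeks |
| ECG | final visit | 8.6.5: over 26 weeks | 32: over 26 weeks |
| C-SSRS | final visit | 8.6.3: no visit named | 29: no visit named |

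For laboratory and ECG, the later text overrides the narrow definition. For C-SSRS nothing visible does, so 2.3.4 is the only visit rule a programmer has.

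**3. Can the Week 26 form recover the early period?** The follow-up form looks back to the last visit. The documents do not say whether that means the last C-SSRS or the last study visit, so both readings are shown.

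- Last C-SSRS: the Week 26 form covers Weeks 8-26, (26 - 8)/26 = 18/26 = 69.2%.
- Last study visit (Visit 8, Week 20): it covers Weeks 20-26, (26 - 20)/26 = 6/26 = 23.1%.

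On neither reading does it reach Weeks 0-8, which are 8/26 = 30.8% of planned treatment. That window contains all scheduled titration: the top dose starts on Day 10 under Amendment 2 (protocol 6.1) and on Day 14 under Amendment 1 (SAP 4.3), which applies to 6 patients (SAP 4).

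On the first reading, the Week 8 form looks back to baseline and so covers titration. On the second, it looks back only to Visit 4 (Week 3, or Week 2 under Amendment 1). Even then it is the only scheduled post-baseline C-SSRS bearing on the first 8 weeks.

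**4. How many assessments could be affected?** Assume 25 patients, all with a Week 8 C-SSRS, and that Table 29 follows 2.3.4 literally. If n of them have a Week 26 C-SSRS, the unused share is n/(25 + n).

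- n = 25: 25/50 = 50.0% (upper bound)
- n = 20: 20/45 = 44.4%
- n = 15: 15/40 = 37.5%

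**5. Illustration, with assumed counts.** If 2 of 25 patients worsened at Week 8 only and all 25 had a Week 26 assessment, the 2.3.4 rule gives 0/25 = 0%. An any-post-baseline rule gives 2/25 = 8%. The documents give no expected event rate.

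**The case against.** The strongest counter-argument is that 2.3.4 is loose wording rather than an operative restriction. The same limit is written there for laboratory and ECG outcomes, and the SAP does not apply it to either. Section 8.6.3 and Table 29 do not exclude Week 8, and SAP Table 4-1 schedules C-SSRS at both visits, so Table 29 could be programmed to show both. This stands as a limit on the claim. A reader might infer that the Week 8 result drops out for every extension patient. The documents do not support that: the output text leaves the visit open, and for an extension patient without a Week 26 C-SSRS no rule is given, so Week 8 might be the value used. But the objection does not remove the problem. Two programmers could produce different Table 29 counts from the same data, and the one written rule points to the final visit.

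Other points in the plan's favour:

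- **Staged analysis.** SAP section 7 plans an analysis of data up to Week 8. No C-SSRS item appears in the available part of its output list, but part of that section is missing from the available text. It cannot be said that Week 8 C-SSRS appears in no output.
- **Adverse events.** The definition in protocol 9.2.11.1 is broad and events are recorded at every visit, so new ideation or behaviour may reach Tables 24-28 or Listing 5. Protocol 9.2.10 does not require a positive C-SSRS to be recorded as an adverse event, so this softens the gap without closing it.
- **Listings.** Section 10.3 has no follow-up C-SSRS listing, but it has no laboratory listing either. The absence is not evidence of a special exclusion.
- **Context.** The study is small and descriptive, and suicidal tendency at screening is an exclusion criterion, so cases may be few. That bears on the likely size of the effect, not on the definition.
- **Protocol grammar.** The 26-week phrase in 4.2.2 could be attached to the ECG item alone. Since 9.2.10 schedules a Week 8 C-SSRS to detect emergence, reading it across the whole list is more natural.

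**Conclusion.** Wrong as written: SAP 2.3.4 defines an outcome narrower than the protocol 4.2.2 parameter it cites, and no visible C-SSRS text repairs it. For patients with a Week 26 C-SSRS, a worsening recorded at Week 8 and resolved by Week 26 does not count under 2.3.4 and may go unreported in Table 29. The Week 26 form cannot make up for this, because Weeks 0-8 (31% of planned treatment, including all scheduled titration) lie outside its recall period.

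The mismatch with the protocol follows from the text alone. The loss of Week 8 data from Table 29 rests on programming that follows 2.3.4. The figure of 25 unused assessments out of 50 further assumes that every patient has both post-baseline assessments, so it is an upper bound. The contrast of 0% with 8% is an illustration, not an expected result.

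**What to change.** Make these changes before Table 29 is produced:

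- **SAP 2.3.4:** define the C-SSRS outcome as worsening from baseline at Week 8, at Week 26, and at any post-baseline assessment.
- **SAP 8.6.3:** name the same three summaries. State that a patient is counted in the last one if either assessment is worse than baseline. An extension patient with no Week 26 C-SSRS then contributes through Week 8.
- **Table 29:** show the three as separate rows for ideation and for behaviour, each with the number of patients assessed as its denominator.

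The cost is a few lines of SAP text and a few table rows. No new data, visits or patient burden are involved. The reported count may be slightly higher than under a final-visit rule, because transient worsening will be included.

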## 5 STUDY POPULATION

### 5.1 *Enrolment and Study Centers*

Approximately 25 patients will be enrolled in multiple centers.

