### **9.2.3 Standard 12-lead Electrocardiogram (ECG)**

A 12-lead ECG will be performed at baseline, and at all in-person follow-up visits. Visits 2 (Day 3), 3 (Day 10) and 4 (Week 3) can only be virtual if an ECG can be performed and transmitted to the site for review.

The ECG after start of study medication will be recorded approximately 5 hours (time window 3.5 – 6 hours) post-morning dose ( $T_{max}$ ) to surveil for deleterious effects on ECG intervals (particularly the QTc interval) and rhythm. Continuation on study drug will be assessed by the investigator or designate dependent on interrogation of the ECG, most importantly the QT interval.

The QT interval can be obtained from the automated measurements of the ECG recorder unless the data quality is poor. In this case, the QT interval is measured from the beginning of the QRS complex to the end of the T wave and averaged over three cardiac cycles. The average QT interval should be corrected for heart rate variability using Bazett's formula ( $QT_c = QT / \sqrt{RR}$ ) or Fridericia's formula ( $QT_c = QT / RR^{1/3}$ ) to create the QTc interval. Each patient should have the QTc measured using the same method on all designated days in the study.

The presence of a bundle branch block (BBB) represents a particular challenge in properly measuring the QTc interval. Following international recommendations, QT interval should be measured in leads showing the longest QT interval, which is usually in right precordial leads. In presence of a BBB, these leads are strongest affected by conduction delay and therefore hamper adequate measurement. A new formula for evaluation of the QT interval in patients with left bundle branch block (LBBB) was introduced in 2014:

$$QT_{mean} = QT_{BBB} - 50\% QRS_{BBB} \text{ (Bogossian et al. 2014)}$$

This formula has proved to be a reliable tool in clinical practice for QTc interval evaluation in patients with LBBB, right bundle branch block (RBBB) or bifascicular block. (Bogossian et al. 2020; Erkacic et al. 2020)

Similarly, ventricular paced rhythm with an increased QRS duration can impact the QT interval. In patients with ventricular paced rhythm, 50ms should be subtracted from the Bazett's formula or Fridericia's formula.(Chakravarty et al. 2015)

If the QTc interval increases to 500 msec or more – or increases 60 msec or more from the baseline recording on any one measurement, this must be reported as an SAE and the study medication must be discontinued.

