## 11 STATISTICAL METHODS

### 11.1 Sample Size Estimation

No formal sample size was calculated for this Pilot study. Approximately 25 patients will be included in this study. Patients who do not tolerate the initial dose of 5 mg/kg of body weight b.i.d. will stay in the study for safety evaluations but will be replaced for the assessment of efficacy.

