### 11.2 Outcome Analyses

Given the small sample size and the design of the study (no placebo comparison), no inferential statistical analyses are planned.

Depending on their distribution, continuous variables will be expressed as mean  $\pm$  standard deviation (SD) or as median (interquartile range [IQR]). Categorical variables will be expressed in counts with percentages.

For all continuous variables, including the NRS pain scores, the change from baseline will be presented as summary statistics.

For categorical variables, summary statistics will be calculated.

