8.6.1 Adverse events (AEs)

The number of adverse events and percentage of patients with at least one adverse event will be summarized by system organ class and by preferred terms (MedDRA).

AEs will be considered as treatment - emergent adverse events (TEAE) if the event onset time (and date) is $>$ start of the IMP. Adverse events with incomplete onset dates will be summarized as TEAE regardless of severity and relationship to the IMP.

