8.6.5 ECG parameters

Descriptive statistics of absolute value and change from baseline of ECG intervals and rhythm during the 26-week study period.

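### SAP 2.3.4 takes ECG and laboratory change at end of follow-up, so off-drug values from patients stopped for QTc or liver findings can pull the mean towards no effect

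*SAP*

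**What the plan says.** **When change is measured.** SAP 2.3.4 names protocol 4.2.2 as its source. It defines the ECG endpoint as "Change (from baseline) in ECG intervals/findings parameters at the end of patient follow-up", meaning the Week 8 or Week 26 visit, and words the laboratory endpoint in the same way. Protocol 4.2.2 lists laboratory changes "as well as ECG intervals and rhythm during the 26-week study period". Later in the SAP, section 8.6.5 plans "Descriptive statistics of absolute value and change from baseline of ECG intervals and rhythm during the 26-week study period", section 8.6.4 summarises laboratory values by follow-up time point, and Tables 30 to 33 are titled for the 26 weeks.

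**Who comes off drug and stays in the data.** Under protocol 9.2.3, if QTc reaches 500 msec or rises by 60 msec or more, "this must be reported as an SAE and the study medication must be discontinued". Protocol 9.2.11.3 requires a stop for potential drug-induced liver injury (DILI). Section 6.5.1 and the Visit 2 text in 9.1 require one for intolerance of the starting dose. Section 6.5.1 keeps patients who stop treatment in follow-up to the end of the trial unless they withdraw consent. The Visit 2 text keeps starting-dose-intolerant patients to Visit 5 for the safety analyses. The safety set (SAP 5.2) is everyone who started drug.

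**Adverse events.** SAP 8.6.1 says "AEs will be considered as treatment - emergent adverse events (TEAE) if the event onset time (and date) is" later than the start of study drug. It sets no closing date after the last dose.

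**The concern.** The stop rules select the patients with the largest QTc and liver changes. At later visits, and at the end-of-follow-up time point, these patients contribute values measured without drug. Protocol 9.2.3 times every post-baseline ECG at 3.5 to 6 hours after the morning dose, a timing with no meaning for a patient no longer dosed. No SAP rule separates those tracings, and the table list has no last-on-drug, largest-on-drug or QTc-threshold output. The only listing of ECG abnormalities (Listing 3) is limited to enrolment.

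The safety objective (protocol 4.2.1) concerns administration at the proposed doses. A mean that mixes dosed and undosed values does not describe that. Where the abnormality has resolved, the error runs towards no effect.

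**Working it through.** **1. Is there a plan figure to reproduce?** No. Protocol 11.1 states "No formal sample size was calculated for this Pilot study" and 11.2 states "no inferential statistical analyses are planned". The documents give no expected QTc change, stopping rate or recovery rate.

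**2. Inputs.**
- n = 25, from protocol 5.1: "Approximately 25 patients will be enrolled in multiple centers".
- Change at the stop: +60 ms, the rise limit in protocol 9.2.3.
- Assumed: k patients stopped (1 to 5), mean change m in the others (10 ms, varied from 5 to 20), and residual change r after stopping (0 for full recovery, 60 for none).

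**3. Formulas.**
- Mean using the last on-drug value: [(25 − k) × m + k × 60] / 25
- Mean at end of follow-up: [(25 − k) × m + k × r] / 25
- Difference: k × (60 − r) / 25. With r = 0 this is 60/25 = 2.4 ms per stopped patient.

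**4. Results with m = 10 and r = 0.**

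| k | Last on-drug mean (ms) | End-of-follow-up mean (ms) | Loss |
|---|---|---|---|
| 1 | (240 + 60)/25 = 12.0 | 240/25 = 9.6 | 20% |
| 2 | (230 + 120)/25 = 14.0 | 230/25 = 9.2 | 34% |
| 3 | (220 + 180)/25 = 16.0 | 220/25 = 8.8 | 45% |
| 5 | (200 + 300)/25 = 20.0 | 200/25 = 8.0 | 60% |

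**5. Sensitivity.**
- Other patients' mean: for k = 1 the loss is 33% at m = 5 (7.2 to 4.8) and 11% at m = 20 (21.6 to 19.2). For k = 5 it is 75% at m = 5 (16 to 4) and 43% at m = 20 (28 to 16).
- Recovery: with k = 2 and m = 10, the end-of-follow-up mean is 9.2, 10.8, 12.4 or 14.0 ms for r = 0, 20, 40 or 60. With no recovery there is no loss.

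**6. Laboratory values.** Assume a mean ALT rise of 0.2 × ULN in 24 patients and +7 × ULN in one who then recovers. The mean falls from (4.8 + 7)/25 = 0.47 to 4.8/25 = 0.19 × ULN.

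**7. Would an on-treatment-only visit table repair this?** Not by itself. With k = 2 and m = 10, dropping the two stopped patients from a late visit moves its mean from 9.2 to 230/23 = 10.0 ms, not to 14.0. The two who reacted most are simply absent.

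**8. Adverse events.** SAP 8.6.1 plans event counts and the percentage of patients with at least one event. Neither can fall when follow-up time is added. A patient who takes drug from the evening of Day 1 to the morning of Day 3 and is followed to Week 8 has about 2 of 56 days on drug. Events in the other 54 or so still count as treatment-emergent, so the open window can only add off-drug events.

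**The case against.** The strongest reply is that these patients are visible elsewhere. Table 32 covers the 26 weeks, and SAP 9.1 includes maximums in every continuous summary, so a large rise at a scheduled visit appears there. Table 31 counts shifts out of the normal laboratory range during the study, and later recovery does not erase them. QTc-rule and potential DILI cases must be reported as SAEs, so they reach Tables 27 and 28 and Listing 5. No table in SAP section 10 is titled as an end-of-follow-up change. The trial is a small descriptive pilot, and it keeps stopped patients in the safety analyses on purpose.

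All of that stands, and it rules out two stronger readings. A reader might infer that patients over the QTc limit disappear from the safety output; the tables just named show otherwise. A reader might also infer that off-drug follow-up dilutes the adverse event results; step 8 shows that it cannot. Nor is every stopped patient off drug for weeks at the last visit, because a finding first made at Visit 9 is an on-drug value. Starting-dose intolerance need not involve any ECG or laboratory change.

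What remains is that an SAE count or a visit maximum does not correct a mean taken after drug was stopped. The SAP also does not say whether unscheduled ECGs, or the repeat liver tests in protocol 9.2.11.3, enter the safety tables; its scheduled-visit rule sits in the efficacy section (8.5).

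**Conclusion.** The point holds in a limited form. SAP 2.3.4 departs from the protocol section that it cites and from SAP 8.6.5. The change that it defines, and the visit means after a stop, mix on-drug and off-drug values. Any resulting bias in the ECG and liver means is towards no effect when the abnormality reverses.

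The size is not knowable from the documents. On the stated assumptions it is 2.4 ms of mean QTc change per fully recovered patient: a 20% to 60% loss for one to five patients with the others at +10 ms, or 11% to 75% if the others' mean lies between 5 and 20 ms. It is zero if nobody stops or nobody recovers. No single figure from this range should be read as a prediction.

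Part of SAP section 7 is not in the available text, so an on-treatment safety item there cannot be excluded; the table list shows none.

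**What to change.** - Reconcile SAP 2.3.4 with protocol 4.2.2 and SAP 8.6.4 and 8.6.5 on the safety period.
- Keep Tables 30 and 32 over all follow-up. Do not make an on-treatment-only visit table the main display, for the reason in step 7.
- Add each patient's last and largest on-treatment change from baseline in ECG intervals and liver tests, including unscheduled tracings and repeat laboratory tests.
- Add counts of patients crossing the protocol's own QTc limits (500 msec; 60 msec rise). Protocol 9.2.3 sets these at or above the limit and 9.2.11.1 above it. The two must be reconciled so that the count has one definition.
- Flag adverse events as on-treatment or post-treatment, using the recorded stop date and a fixed window in days stated in the SAP. Protocol 9.2.11.2 refers to 6 half-lives for pregnancy reporting, but the documents give no half-life, so that wording cannot be applied directly.
- Reconcile protocol 6.5.1 with the Visit 2 text on how long starting-dose-intolerant patients are followed.

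Treatment withdrawal dates are already used in SAP 8.4 and listed in Listing 1, so the analysis changes need SAP wording and programming only. The cost is a few more table rows, and safety changes that may look less favourable.
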